6.2.1 Minimizing Potential Risks

All efforts will be made to minimize these risks by the investigators who are experienced and skilled in endoscopic procedures, clearly defining eligibility criteria to ensure that only the appropriate patients are enrolled and by ensuring that the treatment and follow-up of the patient are consistent with current medical practice. All research procedures will be conducted in the fully equipped facilities, providing access to emergency care and to all necessary precautions to ensure subject privacy. The research procedures will be conducted in a private room, collection of sensitive information about subjects is limited to the amount necessary to achieve the aims of the research, drapes or other barriers will be used for subjects who are required to disrobe.

Stent removal risks are being minimized throughout the study. The Boston Scientific WallFlex™ stent has been carefully selected in order to minimize the risks of tissue ingrowth (7, 9-14) and esophageal damage upon removal. The removal suture will aid in collapsibility of the stent upon removal which will reduce any forceful pulling against the esophageal wall, thusly reducing the likelihood of esophageal abrasion, tear, or perforation. The Investigator will carefully examine the stent for any indications of fracture during and immediately after the removal to ensure no fragments may be remaining in the subject. Data will be collected following each stent removal to document any stent related events. This data will be considered prior to enrolling additional subjects to evaluate the overall safety and potential risk to new subjects.

The Investigator may withdraw a subject from continued participation in this study in the event the procedure cannot be completed (ECM and Stent are not placed), a subject cannot or will not return for stent removal, or if a subject experiences a Serious Adverse Event that compromises his or her ability to undergo follow-up evaluations specified in the protocol.

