3.3 Visit Windows

The following are allowable date ranges for each follow-up period:

Time Point	Date Range
Screening Evaluation and Baseline	Chart Review and Date of Informed Consent up to Day 0
Clearance tests (optional): ECG, PFT, CXR	Within 30 days prior to Day 0
TECR with ECM Placement (Day 0)	Within 60 days of the Screening Evaluation
Day 1	24 hours following Day 0 \pm 6 hours
Week 2	14 days following Day 0 \pm 4 days
Month 1	30 days following Day 0 \pm 7 days
Month 3	90 days following Day 0 \pm 15 days
Month 6	180 days following Day 0 \pm 30 days
Month 9	270 days following Day 0 \pm 30 days
Month 12	360 days following Day 0 \pm 30 days

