3.4.4 Subject Enrollment Procedure

Subjects are enrolled in this study when they have signed the approved informed consent form.

Documentation of the informed consent process will be recorded in the subject's medical record when they are enrolled in the study with the date of entry in the study.

If the inclusion and exclusion criteria during the screening are not met, the subject will not undergo the study procedure even if they have signed an informed consent form. The investigator will also inform the subject that he/she will not undergo the procedure even though they signed the consent. Ineligible subjects will have the option to undergo alternative treatments. The reasons for ineligibility will be captured for all subjects who signed consent.

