3.4.11.2 Contingency Plan – Removal of a Fractured Stent

In previous experiences with removing esophageal stents, poor stent integrity has not been observed. While stent fracturing has not been observed, a contingency plan for coping with this possible outcome will be employed if needed. Several tools may aid in the removal of broken stent pieces. Rat tooth forceps may be used for larger pieces that do not appear to have any sharp edges that could pose risk of abrasion, laceration, or perforation of the esophagus. An EMR retrieval snare could also potentially be used for larger, smooth pieces. An EMR cap with suction could remove any small pieces. The pieces can be suctioned directly into the cap. The cap provides a protective encasement for small fragments and reduces the likelihood of esophageal damage. A Roth Net may be used for any pieces that fall into the stomach. The major benefit of the Roth Net is the protective netting that may prevent any sharp pieces from lacerating the stomach or esophagus upon removal. All extracted pieces will be reviewed outside the body to ensure no fragments remain in the Subject. The investigator will re-introduce the endoscope and carefully view the esophagus, stomach, and duodenum to further ensure no pieces remain inside the body.

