3.4.12.4 Unanticipated Adverse (Device) Events (UAE/UADE)

Per 21 CFR 812.3(s) "an unanticipated adverse device effect means any serious adverse effect on health or safety or any life-threatening problem or death caused by or associated with, a device, if that effect, problem, or death was not previously identified in nature, severity, or degree of incidence in the investigational plan or application, or any other unanticipated serious problem associated with a device that relates to the rights, safety, or welfare of subjects."

If an adverse event is determined to meet the definition of an unanticipated adverse event, the Principal Investigator will immediately conduct an evaluation. An unanticipated adverse device effect that represents an unreasonable risk for subject health or a product performance failure becomes apparent, immediate action will be taken and the appropriate authorities will be notified.

In the event of an unanticipated adverse device effect, which presents an unreasonable risk, for subject's health or a product performance failure becomes apparent, immediate action will be taken and the appropriate authorities will be notified.

Since these are approved devices, any UAE should also be reported to the manufacturer of the product as per user facility reporting requirements at your hospital/institution.

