6.2 Risks

It is anticipated that subjects participating in the study will be exposed to operative and post-operative risks similar to related surgical procedures of the esophagus for the treatment of BE with HGD. Additional risk may include breach of confidentiality as a result of participating in this research study.

Stent removal may pose additional risks that are not fully known at this time. Removal of a fully covered metal stent is not an FDA accepted use of this device.

Potential complications of TECR with ECM placement include, but are not limited to, the following:

- Pharyngolaryngeal pain, temporary abdominal or esophageal pain, post-operative dysphagia due to edema or esophageal stricture, narrowing of the esophagus, nausea, vomiting, musculoskeletal pain (e.g. left shoulder pain), oral or dental injury, and heartburn, are usually mild in severity and may occur in greater than 25% of people.
- Laceration or tear of esophagus, post-operative bleeding, and stent migration are usually moderate to severe in severity and may occur in 1-10% of people.
- This procedure is rarely (less than 1%) associated with severe complications such as pneumothorax, pneumomediastinum, pleural effusion, nerve damage, esophageal perforation, infection in the center compartment of the chest, and arrhythmia. Patients may require conversion to open surgery.
- Failed endoscopic procedure (recurrent disease or narrowing of the esophagus which proves difficult to manage).
- Food bolus impaction is possible due to noncompliance with post-op dietary plan while the stent is in place.
- Allergic reaction to ECM (porcine material). The risks of prolonged contact with porcine derived material such as ECM are not fully known however it is possible that an individual could become sensitized to pork products as a result of this procedure.

Potential complications and complication rates of stent removal post ECM placement are not fully known and may include, but are not limited to:

- Bleeding – bleeding is common however generally subclinical and not severe
- Abrasion – superficial esophageal abrasions are usually visible however they are not typically severe
- Laceration to the esophagus – laceration is rarely observed with stent removal however can pose additional bleeding risk, and pain.
- Perforation of the esophagus

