6.3 Monitoring

A Monitoring Plan will be used as a guide for performing site monitoring visits. This Monitoring Plan will be reviewed throughout the trial and updated as needed with joint approval by the Sponsor/Principal Investigator. The most recent version of the Monitoring Plan will supersede all prior versions.

The clinical site will be monitored to ensure that the Protocol, Institutional Review Board (IRB) approvals and amendments, Good Clinical Practices (GCP), Food and Drug Administration (FDA) regulations (specifically 21 CFR 812.40, 812.42, 812.43, 812.46, 812.100, 812.110, 812.140 and 21 CFR 50, 54, and 56), and other local laws are adhered to throughout the entire course of the study and required follow-up periods.

The occurrence of adverse events will be monitored for each subject on an ongoing basis throughout the study. Unexpected adverse event will be reported immediately to the West Penn Hospital Institutional Review Board (IRB). If an unexpected adverse event occurs, the investigators will re-assess the risk/benefit ratio of the study and submit any modifications deemed necessary to the IRB.

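### The review of stent-removal data in 6.2.1 is tied to enrollment, which 3.4.4 defines as signing consent, so it does not by its terms hold the next procedure

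*Combined protocol and SAP*

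**What the plan says.** Section 6.2.1 (Minimizing Potential Risks) says that data will be collected after each stent removal and adds: "This data will be considered prior to enrolling additional subjects to evaluate the overall safety and potential risk to new subjects". It names no reviewer, no record of the review and no link to Day 0.

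Section 3.4.4 gives the only definition of enrollment: "Subjects are enrolled in this study when they have signed the approved informed consent form". The one thing it says will stop a consented subject from being treated is failure of the eligibility criteria. Section 3.4.10 then has every eligible, consented subject undergo TECR with ECM placement, with no reference to earlier subjects' removals.

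On timing, 3.3 allows the procedure "Within 60 days of the Screening Evaluation", and the stent is removed 14 ± 4 days after the procedure.

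On risk, 6.2 states "Potential complications and complication rates of stent removal post ECM placement are not fully known" and "Removal of a fully covered metal stent is not an FDA accepted use of this device".

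Two other sections can act on a removal event. Section 3.4.12.4: "If an adverse event is determined to meet the definition of an unanticipated adverse event, the Principal Investigator will immediately conduct an evaluation". Section 6.3: "If an unexpected adverse event occurs, the investigators will re-assess the risk/benefit ratio of the study".

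**The concern.** The sponsor chose a safeguard, namely to look at how earlier stent removals went before exposing new subjects. The exposure that matters is the resection and stent placement on Day 0, but the safeguard is attached to the consent signature. A subject who signed before an earlier stent came out has already passed the checkpoint, and nothing in 3.4.4 or 3.4.10 brings that subject back to it.

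The early removals carry information that the plan does not otherwise have. For the five published ECM cases the only stent named is the UltraFlex (3.4.10.2), and the note at the end of section 10 says the UltraFlex in the procedure video has uncovered metal ends. No section reports a WallFlex used with the ECM in a patient. The first removals in this trial are therefore the first reported human evidence on that combination, and a consented subject should have the benefit of it.

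**Working it through.** The plan states no figure on this point, so there is none to reproduce. The check sets the sections side by side and then counts who could be affected.

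**Wording**

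| Step | Section | Event |
|---|---|---|
| Removal data considered | 6.2.1 | before enrolling others |
| Enrollment | 3.4.4 | signing consent |
| Trigger for TECR | 3.4.10 | eligibility plus signed consent |
| Bar to TECR after consent | 3.4.4 | failed eligibility |

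Taken together, these place no hold between consent and Day 0 that depends on another subject's removal.

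**Timing inputs.** Screening to Day 0 is at most 60 days (3.3). Stent dwell is 14 ± 4 days, so 10 to 18 days. N = 10 (5.4). The accrual rate and the interval from consent to procedure are not given; the values below are assumptions.

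**Can consent precede an earlier removal?** Yes. The 60-day window is 60/18 = 3.3 to 60/10 = 6 times the stent dwell.

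**Others stented before the first removal, constant interval from consent to procedure.** Procedures are then spaced like consents. Counting days from the first procedure, the first stent comes out on day 10 to 18.
- One consent per month: the second procedure falls on day 30, so the count is 0.
- Two per month: the second procedure falls on day 15 and the third on day 30. The count is 0 if the stent is out by day 15 and 1 if it comes out later.
- One per week: procedures fall on days 7, 14 and 21, so the count is 1 or 2.

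**Unequal intervals.** Suppose the first subject is treated 30 to 60 days after consent. The first removal is then between day 40 and day 78 from that consent (30 + 10 to 60 + 18).
- Consents every 30 days: 1 to 2 others have signed by then.
- Consents every 15 days: 2 to 5 others have signed.

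These are counts of signatures. They become counts of stented subjects only if every later subject is treated quickly while the first one waits, so they are ceilings. The 78 days also takes the screening date as the consent date; 3.3 lets screening begin with chart review.

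**Consequence.** The documents give no rate for serious removal events. If the rate is p, the first removal goes badly with probability p. At two consents per month and a constant interval, the expected number of others already stented when that happens is at most 1 × p: 0.01, 0.05 or 0.10 for assumed p of 1%, 5% or 10%.

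**Delay from holding only the second procedure.** At monthly spacing it is 0 days. At 15-day spacing it is at most 18 − 15 = 3 days. If the second subject is ready at once, it is 10 to 18 days. Holding all nine later procedures would take 9 × 10 = 90 to 9 × 18 = 162 days if subjects are queued.

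**The case against.** The strongest case is that other text already covers this. A reader might infer from the gap that a perforation or fracture at the first removal would leave consented subjects with no protection. The documents do not support that. Under 3.4.12.4 an effect can be unanticipated because of how often it occurs, even if it is listed. Section 6.2 gives no rate for perforation at removal, and 3.4.11.3 says serious injury at stent removal has not been seen before, so a perforation at the first removal could qualify. The same section calls for immediate action when a product fails to perform, which could include a fracture, although 3.4.11.2 foresees one: "a contingency plan for coping with this possible outcome will be employed if needed". Section 3.4.12.5.1 adds reporting to FDA and the IRB within 10 working days. This much of the objection stands. What remains is that neither 3.4.12.4 nor 6.3 states a hold on consented subjects, and the action to be taken is undefined.

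A reader might also infer that 2 to 5 subjects would be stented unreviewed. That range counts signatures, not procedures.

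Nor do the documents show that the WallFlex is riskier or has never been used with the ECM. Section 3.4.1.2 says its lining is meant to prevent tissue ingrowth, and 3.4.11 mentions earlier removals after ECM placement without naming the model.

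The study has one center and two surgeons, who will know removal results at once, and the stated purpose of protecting new subjects suggests that treating was meant. That is a good reason to write it. The Monitoring Plan (appendix 11.6) is not in this copy, so a stagger rule there cannot be excluded; 6.3 describes it as a guide for site visits.

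**Conclusion.** The mismatch is real and rests on the text alone: the consideration of removal data is tied to consent, and the procedure is not held for it. The text says only that the data will be considered, so it should not be read as an existing formal review requirement.

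The size is small. Under a constant interval from consent to procedure, the number of other subjects stented before the first removal is 0 at one consent per month and 0 or 1 at two per month. Faster accrual or unequal intervals raise it, and the plan sets no limit. These counts rest on assumed accrual and on the 10 to 18 day dwell in the plan. Severity is minor; the case for acting is that the correction costs little and makes the sponsor's own safeguard work as intended.

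**What to change.** In 6.2.1, replace the clause that ties the review to enrolling with: *before TECR is performed in any further subject, including those who have already consented; all stent-removal data available at that time will be reviewed and the review documented, and the second subject will not be treated until the first subject's stent has been removed.*

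The cost is at most one wait of 10 to 18 days after the first procedure, and a short note before each later one. No endpoint, visit or sample size changes. A second subject already close to the 60-day limit might need screening repeated.

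Three further steps are optional. Holding every procedure until the previous stent is out would cost 90 to 162 days in total if subjects are queued. Formal pause rules for perforation or fracture are a design choice for the sponsor. Qualifying reference 7, the five-patient series, where it is cited for fully covered stents would tidy the background, but 3.4.10.2 and the note at the end of section 10 already disclose the change of stent.

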5. STATISTICAL METHODS AND DATA ANALYSIS

This study is a feasibility study in order to assess general efficacy, collect clinical information, make observations, report adverse and serious events, and to provide the basis for possible future applications of TECR with ECM placement. The proposed sample size of 10 is not sufficient to conduct a comprehensive statistical analysis. However, we set forth efficacy and safety objectives in order to standardize our data collection points and outline specific criteria for consideration. Additionally, we have developed a statistical analysis plan that may be useful in future applications of TECR with ECM placement in the event enrollment is increased or extended to include those with T1a esophageal adenocarcinoma.

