5.2.1.1 Parameter of Interest

The parameter of interest is the proportion of subjects with any serious, acute (within 2 weeks post-procedure) adverse events.

5.2.2. Primary Safety Objective 2

To demonstrate the long-term safety of TECR with ECM placement for treatment of BE with HGD by evaluating all study related adverse events occurring more than 2 weeks post procedure through the study endpoint at 12 months post procedure.

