5.4 Size and Duration of Trial

Ten (N=10) subjects will be enrolled in this study. Follow-up on each subject will be 12 months, except in the case of early death, losses to follow-up, or other censoring events.

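### Investigator withdrawal under 6.2.1 can end active safety follow-up for reasons plausibly tied to outcome, so Primary Safety Objective 2 may be under-ascertained

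*Combined protocol and SAP*

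**What the plan says.** Section 6.2.1 (Minimizing Potential Risks) gives the investigator discretion to end a subject's participation on three grounds:

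- "The Investigator may withdraw a subject from continued participation in this study in the event the procedure cannot be completed", explained there as ECM and stent not being placed;
- "a subject cannot or will not return for stent removal";
- "if a subject experiences a Serious Adverse Event that compromises his or her ability to undergo follow-up evaluations specified in the protocol".

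Primary Safety Objective 2 (5.2.2) is to evaluate "all study related adverse events occurring more than 2 weeks post procedure through the study endpoint at 12 months post procedure". Its parameter (5.2.2.1) is a proportion of subjects with a serious late event, and so is the acute parameter (5.2.1.1). Neither section says who is in the denominator or how a withdrawn subject is handled.

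On size, section 5.4 states: "Ten (N=10) subjects will be enrolled in this study". It plans 12 months of follow-up apart from early death, loss to follow-up and other censoring events, and does not define the last of these. Section 3.1 has adverse events assessed at the follow-up time points. The table in section 4 also has a row for adverse events, their follow-up, death and termination, collected on occurrence or on notification.

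**The concern.** The grounds for withdrawal are not neutral with respect to safety. A resection that could not be finished may have stopped because of a complication. A subject who does not return keeps a stent intended for about two weeks, and section 6.2 says of its removal: "Stent removal may pose additional risks that are not fully known at this time". An SAE that prevents follow-up evaluations is itself a poor course. Some cases will be innocent, such as technical failure, refusal or relocation, but the association is plausible enough to plan for.

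Scheduled visits are the only active means of finding adverse events in the visible text. If participation ends, scheduled ascertainment ends with it, and what remains depends on someone telling the site. At stake is the 2-week-to-12-month primary safety result, in a study whose stated purposes include reporting adverse and serious events.

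There is a side effect within 6.2.1 itself. That section says data gathered after each stent removal will be considered before more subjects are enrolled. A subject who never returns for removal supplies none.

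**Working it through.** **Plan's own figure.** There is none to reproduce. N=10 is a feasibility number with no error rate, power, expected safety rate or dropout allowance behind it.

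**Step 1: timing of each ground against the long-term window.** Section 3.3 puts Week 2 at Day 14 ± 4 and Month 12 nominally at Day 360. The long-term window is therefore about 360 − 14 = 346 days.

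- ECM and stent not placed: arises on Day 0. Withdrawal then leaves the whole window unobserved.
- No return for stent removal: arises around Days 10 to 18. Withdrawal at Day 18 leaves 360 − 18 = 342 of 346 days unobserved.
- SAE compromising follow-up: can arise at any time. If it falls in the first 2 weeks, it counts for Objective 1, but the subject may then have no observation for Objective 2. If it falls later and is attributable, the subject already counts for Objective 2 and withdrawal does not change the subject-level proportion.

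The exposure is therefore a first late event that follows withdrawal, not the triggering event.

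**Step 2: what each withdrawn subject leaves open.** Inputs: 10 treated subjects (5.4, assuming that all who enrol are treated); w withdrawn without an observed late event (assumed 1 to 3, since the documents give no figure); e events among the other 10 − w. Intervals are exact Clopper-Pearson 95%, in percent.

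| w | e | Dropped: e/(10 − w) | Kept as no event: e/10 | Kept as event: (e + w)/10 |
|---|---|---|---|---|
| 1 | 0 | 0/9 = 0% (0–33.6) | 0/10 = 0% (0–30.8) | 1/10 = 10% (0.3–44.5) |
| 2 | 0 | 0/8 = 0% (0–36.9) | 0/10 = 0% (0–30.8) | 2/10 = 20% (2.5–55.6) |
| 3 | 0 | 0/7 = 0% (0–41.0) | 0/10 = 0% (0–30.8) | 3/10 = 30% (6.7–65.2) |
| 2 | 1 | 1/8 = 12.5% (0.3–52.7) | 1/10 = 10% (0.3–44.5) | 3/10 = 30% (6.7–65.2) |

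The gap between the last two columns is w/10, or 10 percentage points per withdrawn subject. Two things follow:

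- Dropping a subject does not by itself lower the rate. In the last row it gives 12.5% against 10%. The report is too low only if withdrawn subjects had events that nobody counted.
- If they did, keeping them in the denominator does not help. In the last row the true rate would be 30%, against a report of 12.5% or 10%. A denominator rule alone cannot repair the loss; the events have to be looked for.

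**Step 3: how likely it is to arise.** If each subject has an assumed withdrawal probability p, the chance of at least one in ten is 1 − (1 − p)^10. This is 40% for p = 5%, 65% for p = 10% and 89% for p = 20%.

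**The case against.** A reader might infer that withdrawn subjects leave the analysis, so that the 12-month safety rate is computed only on subjects who did well and is certainly too low. The documents do not support this:

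- Section 6.2.1 ends participation; it does not exclude anyone from analysis. Sections 5.2.1.1 and 5.2.2.1 exclude nobody. Section 5.5.1, which belongs to a possible future analysis of 30 or more, includes all who undergo TECR with ECM placement. The only set conditional on stent removal and a biopsy is the future efficacy set in 5.5.4.
- Section 5.4 does not name investigator withdrawal as censoring. It leaves the residual category undefined.
- Downward bias needs later events that go uncounted, as Step 2 shows.

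Three further objections deserve weight. First, the section 4 row and the duty in 3.4.12.5 to send the IRB follow-up information on reported effects do not stop at withdrawal. That is true, but neither is expressly extended past it, and neither makes the site look for a new event. Second, the case report forms, consent form and monitoring plan are listed as appendices but cannot be seen, and they may address the point. The finding is therefore limited to the visible text. Third, subjects without ECM and stent did not receive the treatment whose long-term safety is being described, so pooling them into that rate is an estimand choice and not a correction. This stands and is reflected in the fix.

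The study is also descriptive. Section 5 says: "The proposed sample size of 10 is not sufficient to conduct a comprehensive statistical analysis". No test or success threshold depends on this rate, which limits the consequence without removing it. Nor does losing study follow-up mean losing care: section 3.4.11.3 provides admission and repeated follow-up after serious injury at stent removal.

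**Conclusion.** The point holds as a risk of under-ascertainment for Primary Safety Objective 2. The withdrawal rule can end active follow-up for reasons plausibly related to outcome, and no visible provision replaces it. The size is 10 percentage points undetermined per withdrawn subject, assuming all ten are treated and in the denominator. With 1 to 3 withdrawn and no event in the rest, the long-term rate is known only to lie between 0% and 10%, 20% or 30%. If fewer subjects are in the denominator, each weighs more (1/9 = 11.1 points with nine).

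The number withdrawn and the occurrence of later events are assumptions; the documents give neither. The direction of any bias is likewise conditional on unseen events. This is a moderate-priority, inexpensive improvement to a feasibility study, and it does not show that the planned analysis is invalid.

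**What to change.** - **6.2.1:** Let the investigator stop the scheduled study EGD and barium swallow visits on the existing grounds, but keep every subject in whom TECR was started in adverse-event and vital-status follow-up. Do this by telephone contact and record review at each scheduled visit date through Month 12, unless the subject withdraws consent. This changes data collection only and leaves clinical care as it is.
- **6.2.3 and the consent form:** Align the wording. Section 6.2.3 limits recorded information to procedures done for the study, which may not cover record review after visits stop.
- **5.2.1.1:** Acute safety denominator: every subject in whom TECR was started.
- **5.2.2.1:** Long-term denominator: every subject who received ECM and stent. Report resected subjects without ECM and stent separately through Month 12.
- **5.4:** Define the other censoring events.
- **Reporting:** List each withdrawal with reason and date. For any subject still lost, give best-case and worst-case bounds as in the table.

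The cost is protocol and consent wording, plus a few calls or chart reviews for perhaps 0 to 3 subjects, with no added procedure or staff. The downside is that safety rates may look slightly less favourable.
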